## **10.7 Stopping Rules for an Individual Subject**

A subject will be discontinued from the study for the following reasons:

- Failure to comply with the protocol
- Develops a serious adverse event (SAE) definitely, probably or possibly related to rifaximin
- Becomes pregnant
- Develops a Grade 3 or greater allergic reaction to rifaximin/placebo or signs and symptoms of an immediate hypersensitivity reaction
- Develops any condition that the study investigators deem would be detrimental for him/her to continue on the study
- Desires to leave the study or withdraws written informed consent
- Presence or occurrence of any clinical adverse event, laboratory abnormality, intercurrent illness, other medical condition or situation occurs such that continued participation in the study would not be in the best interest of the subject.
- Develops any of the exclusion criteria listed in Section 3.4
- Termination of the study by the sponsor
- Requirement for excluded concomitant medications

Subjects who develop a change in condition which requires removal from the study secondary to safety, will be requested to finish protocol visits off drug to assess for safety related concerns.

## **10.8 Replacement of Subjects**

Subjects that discontinue or are withdrawn from the study prior to completion of treatment phases 1 and 2 will be replaced according to the prior randomization.

## **11 CLINICAL MONITORING STRUCTURE**

### **11.1 Site Monitoring Plan**

All research data and results will be carefully recorded using data collection forms that will be saved and allow for continuous access. Further, all collected data will be entered and saved to a password-protected computer spreadsheet (Microsoft Excel™) for analysis and review. The investigator is responsible for assuring that the data collected is complete, accurate and recorded in a timely manner. Source documentation should support the data collected on the CRF and must be signed and dated by the person recording and/or reviewing the data. All data will be annotated and indexed, including all notebooks and computerized information, to facilitate detailed review of data. All data, even those of experiments not directly leading to publication, will be treated comparably. All research data will be made available to scientific collaborators and supervisors for immediate review, consistent with requirements of confidentiality. All research data, including the primary experimental results, will be retained for a minimum of 5 years to allow for analysis and repetition by others of published material resulting from the data. Demographic information and laboratory results will be collected using case report forms and then transcribed into an electronic database on an ongoing basis as participants are enrolled. At the NIH site, data will be stored in the CRIMSON database. Other experimental data, including HIV viral load results, immune activation markers, and gut translocation results, will be analyzed at NCI and reported in batches. Standard laboratory results will be accessed by the local site investigators and the study coordinators. All results, whether recorded on paper or electronically, will be maintained using only the subject's numeric code for identification. Data collection and quality assurance will be performed primarily by the site investigators and study coordinators. RCHSPB will complete onsite monitoring at USUHS, and the University of Pittsburgh including regulatory compliance and source verification.

### **11.2 Safety Monitoring Plan**

#### **Safety Review Plan by the Data Safety Monitoring Board**

This is a double-blind treatment protocol. Monitoring will be performed by the site investigators. The NIAID, USUHS, and the University of Pittsburgh Institutional Review Boards will review the study at least annually. Because of the nature of the study, we plan to constitute a Data Safety Monitoring Board (DSMB) at the NIH to review the study progress and safety at least annually. This function will be provided through NIAID DSMB, and the group will be functioning as a safety monitoring committee for subjects enrolled at all the sites.

The NIAID Intramural DSMB is constituted to review the safety data of Intramural NIAID clinical studies that require DSMB oversight, and consists of experts in infectious diseases, biostatistics, and clinical research. The PI will provide the DSMB Executive Secretary with blinding codes in a sealed envelope in case the DSMB requires this information to make its recommendations. The DSMB will review the protocol prior to opening the study to enrollment and after 50% (22 subjects) complete the first dosing phase of the study and after the second dosing phase. The DSMB will also meet at least once a year to review the completeness of the study data collected and adherence to the protocol in order to evaluate safety, study conduct, and scientific validity and integrity of the study. Other reviews may occur as needed if safety issues arise. All serious adverse events and all unanticipated problems will be reported by the PI to the DSMB at the same time they are submitted to the IRB. The PI will notify the DSMB of any cases of intentional or unintentional unblinding as soon as possible. The PI will notify the Board at the time pausing or halting criteria are met and obtain a recommendation concerning continuation, modification, or termination of the study. The PI will submit the written DSMB summary reports with recommendations to the IRBs. At the WRNMMC an independent medical monitor will also monitor the study; their role is detailed in Appendix E.

#### Emergency Un-blinding Procedures

In the event of a medical emergency or in the event an off-study criterion is met where knowledge of the treatment will affect medical management, the investigators can break the blind. To break the blind investigators will contact the pharmacy department by pager and via electronic mail, as they will hold the randomization code. In the rare event of such an occurrence the process will be documented in writing. The DSMB Executive Secretary will be notified of the unblinding within 1 business day. If the DSMB decides to terminate the study, the blind will be broken and study subject and their primary care physician will be informed of their drug assignment.

## **12 STATISTICAL CONSIDERATIONS**

### **12.1 Study Hypotheses**

This is a double-blind, randomized, crossover, placebo-controlled trial of rifaximin use in HIV-infected subjects. In this trial, ART-treated subjects with an undetectable viral load will be enrolled. The primary objective of this study is to compare the changes in sCD14 levels during the rifaximin phase of the study and compare it with the changes in sCD14 during the placebo phase of the study. Specifically the difference in sCD14 levels measured on Days 28 of treatment phase 1 and 2 will be used to assess rifaximin effect. Moreover to deal with a possible secular trend, the difference of differences (the difference of sCD14 levels measured on treatment phase 1 Days 0 and 28 and the difference measured on treatment phase 2 Days 0 and 28) will be examined as well.

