## Protocol Summary

Title:	A Double Blind Randomized Placebo-Controlled Study Examining the Effects of a Non-Absorbable Antibiotic (Rifaximin) on the Chronic Immune Activation Observed in HIV-Infected Subjects
Short Title:	The Effect of Rifaximin on Immune Activation in HIV-Infected Subjects
Clinical Phase:	IIb
Conducted by:	National Institute of Allergy and Infectious Diseases
Principal Investigators:	NIH: [name] NNMC: [name] University of Pittsburgh: [name]
Sample Size:	44 subjects completing both dosing phases
Accrual Ceiling:	N = 200 subjects. It is anticipated that about 1 in 4 patients with an undetectable viral load on standard testing will have a detectable viral load on the single copy assay. Hence, to recruit 44 patients we anticipate screening approximately 200 patients
Study Population:	Suppressed HIV-infected adult subjects currently on antiretroviral therapy (ART)
Accrual date:	Accrual will be completed 2 years from enrollment of the first subject
Study Design:	Utilizing a randomized, double-blind, placebo-controlled study, with a case cross-over study design, we will assess the effects of rifaximin on markers of lipopolysaccharide (LPS) bioreactivity, cellular markers of activation, and microbial translocation.
Study Duration:	We anticipate that accrual and follow up will be completed over a 3 year period. Each participant will be in the study for 18 weeks
Study Agent:	Rifaximin

**Intervention Description:** Oral rifaximin at a dose of 550 mg twice daily will be administered for 4 weeks to HIV-infected subjects who are virologically suppressed on ART

**Primary Objective:** The primary objective of this study is to compare changes in soluble CD14 (sCD14) levels (a marker of monocyte activation and LPS bioreactivity) during the rifaximin phase of the study and compare it with the changes in sCD14 levels during the placebo phase of the study in HIV-infected aviremic subjects

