### **3 STUDY DESIGN**

#### **3.1 Description**

The study will be conducted as a randomized, double-blind, placebo-controlled trial and utilize a case cross-over design. In such a study design each subject serves as his or her own control. Such a study design avoids issues related to the inter-individual variability associated with response to treatment. Both the primary and secondary objectives will be evaluated in ART-treated subjects who have suppressed viremia as measured by standard assays. Subjects will be initially randomized to receive a 4 week course of rifaximin or placebo. Upon completion of a 4 week course of rifaximin or placebo they will undergo a 4-6 week washout period and cross over treatment assignments to complete a 4 week course of either rifaximin or placebo. The duration of 4 weeks was chosen as studies in cirrhotic patients suggest that both plasma endotoxin levels and biomarkers of inflammation show statistically significant declines, ~50%, after 28 days of rifaximin therapy [100-101]. Both these studies also used a dosage of 1200 mg. In this study, we will be using a 1100 mg dose as the drug is approved at a 550 mg dose. A 4-6 week washout period was chosen as studies in subjects with ulcerative colitis suggest that the concentration of intestinal microbial groups return to initial values after approximately a 4 week wash-out following rifaximin therapy [101-102].

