#### **Research Labs**

- Immunophenotyping to include a CD4 count and cellular markers of activation (including HLA DR, CD38, co-expression of HLA DR and CD38 on CD4 and CD8 cells)
- Single copy assay and HIV-1-RNA levels
- Soluble markers of inflammation (interleukin6 [IL6], highly sensitive C reactive protein [hsCRP], tumor necrosis factor [TNF $\alpha$ ], D-dimer)
- Markers of bacterial translocation (LPS, bacterial 16S rDNA/bacterial RNA, soluble CD14 [sCD14])

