### **12.2 Sample Size Justification**

In a sub-analysis of the SMART study, baseline sCD14 levels predicted mortality; those who died in the SMART study had a baseline median sCD14 level of 2.47 pg/mL \*10^6

(IQR 2.19 – 2.91), while matched controls had lower levels at 2.23 pg/mL \*10^6 (IQR 2.01 -263). As these differences were statistically significant, we powered our study to exhibit a similar effect size [55].

With a mean of 2.45 pg/mL\*10^6 and a standard deviation of 0.45 pg/mL\*10^6 observed in ART treated subjects in the SMART study (personal communication [name]) and a correlation coefficient of 0.71 (personal communication [name] and [name]), a trial with a total of 40 aviremic patients has a power of 95% (with type I error of 0.05 based on a one-sample paired difference t test) for detecting a 0.20 difference in sCD14 levels between the placebo and rifaximin phases (namely Day 28 and 84) of the study. Due to possible loss to follow-up (10%), 44 patients will be accrued in this study.

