### 12.3 Description of the Statistical Methods

This is a double-blind, randomized, crossover placebo-controlled trial of rifaximin use in aviremic HIV-infected subjects.

The primary goal of this study is to compare the sCD14 levels during the rifaximin and placebo phases of the study. Patients who receive steroids or an additional antibiotic during a treatment period will have a pause and then restart the treatment for a complete period (as described on page 29). Thus such patients will have the endpoints measured at the end of each of the two periods and will be included in the primary analysis. A sensitivity analysis will be conducted where such patients are excluded.

Forty-four aviremic subjects will be randomized to either rifaximin followed by placebo or placebo followed by rifaximin (22 per sequence). The following table displays the treatment and control sequence for the study.

Treatment phase 1	Washout	Treatment phase 2
Day 0-28		Day 0-28
22 aviremic subjects receive rifaximin initially	Washout	22 aviremic subjects switch treatment assignments and receive placebo.
22 aviremic subjects receive placebo initially	Washout	22 aviremic subjects switch treatment assignments and receive rifaximin

At the end of this trial, one sample Wilcoxon statistic will be applied to evaluate the primary end points (difference on Days 28 of treatment phase 1 and 2 of the study). The primary endpoints of interest are changes in soluble CD14 levels between the rifaximin and placebo phases of the study. A P value less than 0.05 will be used to claim significance [114]. Statistical tests and confidence intervals will be two sided.

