### **Secondary outcomes for statistical considerations**

In the following paragraphs the term paired difference refers to the difference between Days 28 of treatment phase 1 and 2. These differences will be tested using both the Wilcoxon test and the t-test.

The following paired difference will be examined between the placebo and the rifaximin phase of the study

1. Changes in HIV-1-RNA levels
2. Changes in Serum LPS levels
3. Changes in the proportion of CD8+HLADR+, CD8+CD38+, CD8+HLADR+CD38+, CD4+HLADR+, CD4+CD38+, and CD4+HLADR+CD38+ cells.
4. Changes in the soluble markers of inflammation (IL6, TNF $\alpha$ , D-dimer, and hsCRP)

In addition to deal with a possible secular trend, the difference of differences (for example the difference in HIV-1 RNA levels measured on Days 0 and 28 of treatment phase 1 and treatment phase 2) will be examined as well.

The proportions of different types of adverse effects as well as 95% confidence intervals will be reported.

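### The supportive secular-trend analysis of sCD14 subtracts Day 0 in full and ignores the randomized sequence; comparing the sequences is more precise from the same samples (low priority)

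*Combined protocol and SAP*

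**What the plan says.** The primary contrast is clear. Section 12.1 states: "Specifically the difference in sCD14 levels measured on Days 28 of treatment phase 1 and 2 will be used to assess rifaximin effect". Section 12.2 sizes the trial for "a 0.20 difference in sCD14 levels between the placebo and rifaximin phases (namely Day 28 and 84"), and section 12.3 says that a "one sample Wilcoxon statistic will be applied to evaluate the primary end points".

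For a time trend, section 12.1 adds a second look: "Moreover to deal with a possible secular trend, the difference of differences", meaning the Day 0-to-28 change in phase 1 against the same change in phase 2. Section 12.3 repeats this for the secondary outcomes: "In addition to deal with a possible secular trend, the difference of differences". For sCD14 no test, power or decision rule is attached to it.

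Patients are randomized 22 per sequence, but section 12 contains no sequence or period term, no between-sequence comparison and no baseline covariate. The Day-0 data exist: the research laboratory list for Day 0 includes "Markers of bacterial translocation (LPS, bacterial 16S rDNA/bacterial RNA, soluble CD14 [sCD14"]), and the phase-2 Day 0 list in section 5.6 includes sCD14 as well.

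**The concern.** Full subtraction fixes the weight on Day 0 at one, whatever the data show. When the Day-0 and Day-28 differences are weakly correlated, this adds noise. With equal SDs, the difference of differences is less precise than the plain Day-28 difference whenever c is below 0.5.

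Subtraction also cancels a drift within a patient only if the drift is the same over both four-week phases. A step between phases leaves a residual whose sign depends on sequence. Comparing the randomized sequences removes an additive period effect of any shape.

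With adequate washout, both analyses target the same effect. A noisy trend check can therefore be non-significant after a true positive primary result through chance alone, and a reader could mistake that for evidence of a trend. What is at stake is how far the trend check can be relied on.

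**Working it through.** **Inputs from section 12.2.** SD 0.45, correlation 0.71, effect 0.20 (all sCD14 in units of 10^6 pg/mL), n = 40, alpha 0.05. Section 12.3 makes tests two-sided. The Protocol Summary sets the sample at 44 completers, so n = 44 is shown too.

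**The plan's own figure.** SD of the Day-28 difference: s = 0.45 × √(2 × (1 − 0.71)) = 0.3427. Noncentrality: 0.20 × √40 / 0.3427 = 3.69. A paired t test with 39 df has power 94.9%. The stated 95% reproduces.

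**The unknown.** c is the correlation between (phase-1 minus phase-2) at Day 0 and the same difference at Day 28. It is an assumption:
- If 0.71 applies between every pair of visits, c = (0.71 − 0.71 − 0.71 + 0.71)/0.58 = 0.
- If correlation decays with time and equals 0.71 between the two Day-28 visits, a 4-week washout (visits at weeks 0, 4, 8, 12) gives c = (0.71^0.5 − 0.71^1.5)/0.58 = 0.42. A 6-week washout (weeks 0, 4, 10, 14) gives c = (2 × 0.71^0.4 − 0.71^1.4 − 0.71^0.6)/0.58 = 0.54.

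**Formulas, with equal Day-0 and Day-28 SDs (assumption).**
- Difference of differences: SD = s√(2(1 − c)), which is 0.4847 / 0.4055 / 0.3427 at c = 0 / 0.3 / 0.5; df n − 1.
- Between-sequence, no Day-0 term: SD = s, df n − 2. Power is 94.9% (n = 40) or 96.6% (n = 44) at any c.
- Between-sequence, adjusted for the Day-0 difference: variance s²(1 − c²)(1 + 1/(n − 4)), df n − 3. The last factor is the cost of estimating the slope.

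| c | Difference of differences, n = 40 | Adjusted, n = 40 | Difference of differences, n = 44 | Adjusted, n = 44 |
|---|---|---|---|---|
| 0 | 72.1% | 94.4% | 76.3% | 96.2% |
| 0.3 | 86.0% | 96.0% | 89.2% | 97.5% |
| 0.42 | 91.7% | 97.4% | 94.0% | 98.4% |
| 0.5 | 94.9% | 98.4% | 96.6% | 99.1% |
| 0.54 | 96.2% | 98.7% | 97.5% | 99.3% |

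Simulation with bivariate normal data and equal sequences agreed with these figures.

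**Where the advantage ends.** At n = 40 the two are equally precise when 2(1 − c) = (37/36)(1 − c²), so c = 72/37 − 1 = 0.95. If the Day-0 differences have 0.8 times the SD of the Day-28 differences (assumption), the adjusted model leads only up to c = 0.68. From there to 0.88 it is slightly worse, by at most about 1.4% in standard error. Compared with the plain Day-28 difference, adjustment brings no gain for c below 0.16.

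**Disagreement with a positive primary.** Simulated at n = 40 with a true effect of 0.20 and a significant primary Wilcoxon test: the difference of differences is non-significant in 24.4 / 11.5 / 3.9% of trials at c = 0 / 0.3 / 0.5, and the adjusted comparison in 1.1 / 0.9 / 0.4%.

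**Incomplete washout.** Suppose 25% of a 0.20 effect remains at phase-2 Day 0 and is gone by Day 28 (assumption). Full subtraction is biased by 0.25 × 0.20/2 = 0.025 and estimates 0.225. The adjusted model is biased by c times that and estimates 0.2075 (c = 0.3) to 0.2125 (c = 0.5). Without the Day-0 term the bias is zero.

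**The case against.** The plan contains no error here. The difference of differences is an additional look with no decision rule. Balanced sequences already cancel an additive trend from the mean Day-28 difference, and an assumed shift of 0.1 or 0.2 lowers the power of the primary comparison (t test) only from 95% to 94% or 90–91%. This stands, and it is why the priority is low.

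The size depends on a correlation that the documents do not give. The 72% figure belongs to c = 0. Under time decay the gap is 91.7 against 97.4% or 96.2 against 98.7%, and it is smaller again with 44 completers. This stands.

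At low c the gain comes from comparing sequences, not from the Day-0 covariate, which costs about 0.6 points against the plain Day-28 difference at c = 0. This stands, so both versions should be reported.

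The low disagreement rates of the adjusted model partly reflect its closeness to the primary statistic. Non-significance is also a mild form of disagreement: simulated with 44 patients and a significant primary, the difference of differences had the wrong sign in under 0.1% of trials. Those rates show the noise in full subtraction; they do not show that the alternative is an independent check.

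The objective is worded as a comparison of changes, and the difference of differences is the only planned sCD14 analysis of within-phase change. It should therefore stay.

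**Conclusion.** The point holds as a precision improvement to a supportive analysis. Full subtraction gives 72 to 96% power over c = 0 to 0.54 at n = 40 (76 to 98% at n = 44). The adjusted between-sequence model gives 94 to 99% (96 to 99%), and the unadjusted one 94.9% (96.6%) at any c. The figures assume normal data and equal Day-0 and Day-28 SDs, and they apply to sCD14 only.

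Two stronger readings are not supported. A reader might infer that the trial is underpowered or that its primary conclusion is at risk from a trend; the stated power reproduces and the primary test does not use Day 0. A reader might also infer that most enrolled patients will have undetectable HIV-1 RNA, so that HIV-1 RNA cannot be analysed this way, because the Protocol Summary expects that "about 1 in 4 patients with an undetectable viral load on standard testing will have a detectable viral load on the single copy assay". That figure is used there to explain why about 200 people would be screened to recruit 44. It does not describe those enrolled, and the eligibility criteria in section 3.4 set no single-copy threshold.

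**What to change.** In section 12.1, add wording to this effect:

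> For a possible secular trend, a supportive linear model will compare Day-28 sCD14 in phase 1 minus phase 2 between the randomized sequences, adjusted for the corresponding Day-0 difference. Half the sequence coefficient estimates the rifaximin-minus-placebo difference. The model will also be reported without the Day-0 term.

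Keep the difference of differences as a labelled sensitivity analysis. Leave the primary one-sample Wilcoxon test of the Day-28 difference unchanged. The same model may be used for continuous secondary markers on a suitable scale, with no power claim, since the documents give no SDs for them.

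State that phase-2 Day 0 follows phase-1 treatment, so the adjusted version relies on washout. The washout rationale in section 3.1 is that "the concentration of intestinal microbial groups return to initial values after approximately a 4 week wash-out following rifaximin therapy"; it concerns gut bacteria, not sCD14. The version without Day 0 does not need washout to be complete by phase-2 Day 0.

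The cost is wording only: no extra patients, visits or samples. The model uses up to two degrees of freedom (39 to 37 at n = 40), about 0.6 points of power against the plain Day-28 difference at c = 0. If washout is incomplete, the adjusted version carries a small bias, less than that of full subtraction for c below 1.
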